This study will be a double-blind, randomized, placebo controlled trial, evaluating drug-free inpatients (at least 24hs period pre-admission) with depressive episode associated with past suicidal attempt and current active suicidal ideation. Patients will be randomly assigned to intranasal ketamine hydrochloride (50 mg) or saline solution (1 to 1 in both groups, suicide or suicide plus alcohol, with a total of 4 groups). After the single intranasal administration, assessments will occur at +40 min, +240 min, +24 h (phase 1), and +48 h (phase 2). For phase 2, patient may receive their regularly scheduled daily medications if improvement less than 50%. Pts will be subsequently followed up on the suicidal ideation scores until discharge once a day with treatment as usual. This study is expected to take one year to be concluded. Medication should be applied in the first 24hs after admission. There is no approved treatment for suicidal ideation and just a few trials used ketamine for suicidal ideation, none of them evaluating the intranasal route. Thus, a placebo-controlled study is warranted to prevent potential methodological issues. The use of ketamine plus standard care would bias the evaluation of the specific antisuicidal efficacy of intranasal ketamine since standard treatments in some cases may also target suicidality and mood in the short-term.

Assessment of antisuicidal efficacy will be obtained using the Columbia-Suicide Severity Rating Scale (CSSRS) as a screening tool for inclusion (based on "yes" or "no" questions) at HCPC. MADRS item 10 score of 5 or 6 suggests active suicidal risk and will be also used as the threshold for patient inclusion in the ketamine intervention. For those enrolled, the primary efficacy outcome measure will be changes in suicide severity at 24hr post-treatment based on the Scale for Suicide Ideation (SSI) scores, which assesses presence of suicidal ideation and history of suicidal behavior. Secondary outcomes to be administered at each visit include the Montgomery-Åsberg Depression Rating Scale (MADRS), the Young Mania Rating Scale (YMRS), the Clinician-Administered Dissociative States Scale (CADSS), Snaith-Hamilton Pleasure Scale (SHAPS) Alcohol Urge Questionnaire (AUQ) and the Clinician-Administered National Institutes of Health-Brief Fatigue Inventory (NIH-BFI). Inter-rater reliability will be assessed for all ratings, with accepted kappa over 0.8.

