- 5) *Clinician-Administered Dissociative States Scale* (CADSS) is a clinician-administered measure of perceptual, behavioral and attentional changes occurring during dissociative experiences that has been tested in healthy subjects and post-traumatic stress disorder (PTSD). This scale involves 19 self-reported questions and eight observer ratings scored from 0 (not at all) to 4 (extremely). To characterize dissociative responses to ketamine, the CADSS will be sorted into five subscores with apparent face validity based on published scales that also assess dissociative states: body perception, environmental perception, feelings of unreality, memory impairment and time perception (Bremner et al 1998).
- 6) The *Snaith-Hamilton Pleasure Scale* (SHAPS) is an assessment of anhedonia, which has been extensively used by our group. The 14-item measure takes 5 minutes to complete (Snaith et al 1995).
- 7) The *Clinician-Administered National Institutes of Health-Brief Fatigue Inventory* (NIH-BFI) is an assessment of fatigue in the context of depression (Saligan et al 2015).
- 8) *Self-Report: Alcohol Urge Questionnaire* (AUQ) is a multi-item measure of self- reported urges to drink alcohol, predictor of drinking abuse and relapse (Bohn MJ, Krahn DD, Staehler BA 1995) and AUDIT/CIWA.

Although the primary aim of this study to investigate the efficacy of ketamine as a treatment for suicidal thoughts, this investigation is also designed to provide initial data for potential biomarkers of antisuicidal response and the neurobiology of the response process. Sixty six percent of all patients will

IRB NUMBER: HSC-MS-17-0903
IRB APPROVAL DATE: 10/09/2019

receive intranasal ketamine, while only 33.3% will be receiving placebo. We decided not to use active placebo (midazolam) due to the risk of increasing craving for alcohol. After the end of the trial (48hs), all patients will receive treatment as usual as well as lithium, which is a medication that has shown significant antisuicidal properties (Lewitzka et al 2015). All patients will be discharge when presenting no acute suicidal ideation based on C-SSRS and SSI.

Study Population

All study investigators and raters will be blind to assignment. Subjects will complete an informed consent process and will be systematically screened for inclusion and exclusion criteria, as follows:

Inclusion Criteria:

1. Male or female between the age of 21 and 60 years old, voluntary admission.

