Intranasal ketamine will be prepared as 100mg/ml ketamine in 0.9% saline or saline alone. An LMA MADgic mucosal atomization device will be used to provide 5 intranasal applications of solution (volume 100 μ l), separated by 3 minutes. Each of five ketamine applications will provide 10 mg of study drug. Ketamine administrations will be provided over 15 min by the principal investigator or attending psychiatrist in a psychiatric unit. Patients will be monitored for at least 4 hours in the psychiatric unit (observation room at 2D unit) after ketamine/placebo administration, including continuous monitoring of vital signs (i.e., heart rate, blood pressure, respiration, and pulse oximetry). The proposed dose does not induce sedation/anesthesia (the required dose for sedation would be 6-9mg/Kg) and here the dose to be used in 6 to 18 times lower than the sedation dose (between 0.5-1mg/Kg). Besides, the investigator has extensive experience using the proposed dose, with no reports of any serious adverse effect in a sample of over 100 patients.

Ratings of suicidal thoughts, depression, anxiety, anhedonia, fatigue, dissociation and other clinical symptoms will be collected during this trial, at the following time points: baseline (pre-ketamine), then 40 and 240minutes, 1 day and day 2 (+48h) post-ketamine. Blood will be collected at the same timepoints, except for 40 minutes and 48 hours post-ketamine.

In order to ensure pregnant women are excluded from the study, a urine pregnancy test will be performed on female patients that meet all other inclusion criteria. We will also collect blood for the purpose of transcriptional profiling, metabolomics, proteomics, and the measurements of inflammatory measures including cytokines and kynurene pathway metabolites. We will also evaluate Brain-derived

IRB NUMBER: HSC-MS-17-0903
IRB APPROVAL DATE: 10/09/2019

neurotrophic factor (BDNF) as well other neurotrophic factors and cytokines in plasma and mRNA expression. Our recent studies support the role of these markers in depression (Zarate and MachadoVieira 2017) and the present investigation will address the effects in suicidal ideation. Samples will be collected via antecubital intravenous line. Samples will be collected via venipuncture. If sample collection is difficult via venipuncture a PIV catheter may be used for no more than 24hrs in order to decrease discomfort.

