The Principal Investigator will be responsible for knowing the policies of the local IRB (the UT – Houston Committee for the Protection of Human Subjects, CPHS). The PI will adhere to CPHS policies and maintain accurate documentation of CPHS correspondence and reports (e.g., annual report). The Principal Investigator (PI) is responsible for detecting, documenting, and reporting unanticipated problems, adverse events (AEs), including serious adverse events (SAEs), and deviations Relatedness to the research of all serious adverse events will be determined by the PI. Dissociation with ketamine does not last more than 40 minutes after ketamine use in Depression and its presence has been associated with a better rapid antidepressant response (Luckenbaugh et al 2014). We expect that dissociation does

IRB NUMBER: HSC-MS-17-0903
IRB APPROVAL DATE: 10/09/2019

not affect the anti-suicide efficacy, being mild and transitory (if present) using the safer intranasal route. In addition, all patients will be strictly monitored at the hospital for at least 48hs after ketamine use, which provides safety for all patient, either responders or not.

There are minimal risks to subjects involved in this study related to the participation in this study. The proposed dose (50 mg) has been safely given to human subjects in previous clinical trials. Ketamine was well tolerated at low doses, with the most common side effects being transient and limited. Based on a similar study evaluating the same dose of intranasal ketamine for depression (Lapidus et al 2014), ketamine was well tolerated with showed minimal psychotomimetic or dissociative effects as well as was not associated with any clinically significant change in hemodynamic parameters. The same findings were observed in additional studies using intranasal ketamine in chronic pain (previously described). Based on previous evidence we do not expect ketamine to impair cognitive functions such as memory, attention and language (aan her Rot et al., 2010). Thus, we considered that intranasal ketamine in the proposed dose will be safe and well-tolerated. Besides, the PI has extensive experience with ketamine in terms of safety and efficacy from the trials he has done at the National Institutes of Health. Patients will follow all routines at the unit after the initial 4hs of initial observation (groups, etc).

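### The first post-dose CADSS is at +40 min, the protocol's own upper limit for ketamine dissociation, and no recall window is stated, so a low score may not show that dissociation was mild

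*Combined protocol and SAP*

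**What the plan says.** **Timing.** Under Study Procedures, dissociation is among the ratings taken at "baseline (pre-ketamine), then 40 and 240minutes, 1 day and day 2 (+48h) post-ketamine". The Design section gives the same post-dose times: "After the single intranasal administration, assessments will occur at +40 min, +240 min, +24 h (phase 1". It lists the CADSS among the outcomes given at every visit. No CADSS is listed between dosing and +40 min.

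**Dosing.** The sprays are "separated by 3 minutes. Each of five ketamine applications will provide 10 mg of study drug", and the whole administration is said to take 15 minutes.

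**Expected course.** Data and Safety Monitoring states that "Dissociation with ketamine does not last more than 40 minutes after ketamine use in Depression". It then expects that dissociation does "not affect the anti-suicide efficacy, being mild and transitory (if present) using the safer intranasal route".

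**The instrument.** Clinician Administered Measures describes the CADSS as covering "perceptual, behavioral and attentional changes occurring during dissociative experiences". It adds: "This scale involves 19 self-reported questions and eight observer ratings scored from 0 (not at all) to 4 (extremely". Its purpose here is stated too: "To characterize dissociative responses to ketamine, the CADSS will be sorted into five subscores". No reference period is given. The Design section names the CADSS and the YMRS mood item as the specific safety and tolerability measures, and the Hypothesis section predicts that the 50 mg nasal dose will be well tolerated.

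**The concern.** The scale meant to describe the dissociative response is first applied when, by the protocol's own statement, that response should be over. A current-state score at that time looks much the same whether the patient felt almost nothing or had a marked episode that had already passed. The expectation in the safety section has two parts, short duration and low intensity. The schedule can check the first but may not check the second.

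At stake is the dissociation component of the tolerability conclusion, along with the five CADSS subscores. The expectation that dissociation does not influence the antisuicidal effect would also be hard to examine with a score taken after the episode. The gap is in data collection, so no later analysis can fill it.

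**Working it through.** The plan gives no figure to reproduce here. The check sets the clock times side by side and asks what a score at +40 min can distinguish.

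**1. Dosing clock (Study Procedures).** Five sprays 3 min apart fall at 0, 3, 6, 9 and 12 min. The last spray is at 12 min, or dosing ends at 15 min on the stated total.

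**2. Rating time against the 40-minute limit.** Neither has a stated time zero, so there are four combinations. The gap is the rating time minus the limit, in minutes from the first spray. Figures in brackets use 15 min as the end of dosing.

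| Rating counted from | Limit counted from | Gap |
|---|---|---|
| first spray | first spray | 40 − 40 = 0 |
| end of dosing | end of dosing | 52 − 52 = 0 (55 − 55 = 0) |
| first spray | end of dosing | 40 − 52 = −12 (40 − 55 = −15) |
| end of dosing | first spray | 52 − 40 = +12 (55 − 40 = +15) |

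These readings are not equally plausible. The Design section places the assessments after the administration, which favours counting the rating from the end of dosing. If the limit is counted from the same point, the gap is 0. Only the third row puts the rating inside the window, and even there it comes 40 − 12 = 28 min after the last spray.

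**3. What a current-state score can distinguish.** If all items are summed, the CADSS runs from 0 to 27 × 4 = 108. Take the protocol's statement at face value, with the rating at or after the limit. The drug-related part of the score is then 0 for any earlier peak, from trivial up to 108. This follows directly from the premise and needs no assumed curve. The converse does not apply: a high score at +40 min would still be informative, and a low one does support short duration.

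**4. What recall could restore.** The 19 self-report items carry 19 × 4 = 76 points and can be asked about the time since dosing. The 8 observer items carry 8 × 4 = 32 points (32/108 = 30%) and need someone who was present. If raters already ask about the whole period, most of the concern goes. The plan does not say that they do, although the same list of measures gives a since-last-visit version for the C-SSRS and asks for both current and worst-point thoughts on the SSI.

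**5. Size.** How much of the peak is missed depends on when nasal dissociation peaks and how it fades. The documents give neither, so no percentage is offered. If the nasal peak falls at about +40 min, nothing is lost.

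**The case against.** **Other recording exists.** The Design section says dissociative adverse effects will be measured. Under Procedure in case of adverse events, the definition covers any untoward occurrence linked in time to the drug, and all events are graded for severity. Staffing is one-to-one in the first hour. Marked dissociation before +40 min therefore has a route to a graded record. This stands as partial cover, but it gives neither a CADSS score nor subscores. A reader might infer that non-serious dissociation goes unlogged, because one sentence mentions expected side effects only when serious. The broad definition beside it does not support that inference.

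**Silence on recall is not current-state scoring.** The wording on the CADSS describes what is measured, not when it must be asked, and would fit questions about an episode just ended. This stands, and it is why the point is conditional.

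**The 40-minute limit is borrowed.** It comes from a cited study not shown to be of nasal dosing; the Background describes related work with intravenous infusion. This stands. A reader might infer that the schedule misses peak dissociation, or that a low score cannot bear on mildness at all. Without a nasal time course, the documents do not support either statement.

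**Little depends on the CADSS.** The plan has no CADSS threshold, no CADSS stopping rule and no named CADSS analysis in the Statistics section. This stands and limits the severity. The scale is nonetheless a named tolerability measure.

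**Conclusion.** The point holds as a minor, conditional one about data collection. If the CADSS is scored for the current state, a low value at +40 min supports short duration but may not show low intensity, so it would be weak evidence for the dissociation part of the tolerability hypothesis.

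This rests on three things: the protocol's own 40-minute statement applying to the nasal route, no recall window being in use, and the rating falling at or near that limit. The amount lost is unknown.

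A reader might go further and conclude that the tolerability hypothesis as a whole is untestable or that efficacy is compromised. The documents do not support that. Vital signs, the YMRS mood item, adverse-event grading and bedside observation address other harms and some marked dissociation, and the primary SSI outcome is unaffected.

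**What to change.** 1. State time zero for all post-dose ratings. The first spray is the simplest choice.
2. At the existing +40 min visit, score the CADSS twice: once for the current state and once for the worst state since the first spray. Have the observer items of the worst-state score rated by staff present since dosing.
3. Report the worst-since-dosing change from baseline, by arm, as the tolerability measure. Describe a current-state score at +40 min as residual dissociation only, including for patients who have no other early score.
4. Optionally, add one brief CADSS at about +20 min from the first spray (20 − 12 = 8 min after the fifth), using the staff already at the bedside.

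**Cost.** Items 1 to 3 need a few sentences, no new visit and no new staff, since one-to-one cover in the first hour is already planned. The second scoring adds some rating time (the plan gives no administration time for the CADSS) and relies on short recall. Item 4 adds one rating per patient: 60 at the stated total enrolment, or 45 if the described groups of 30 and 15 apply. Closer questioning about dissociation slightly raises the risk of unblinding, although the bedside team, who also do ratings, would see acute effects anyway. A separate SSI rater would reduce that risk, but it is an extra staffing demand and is not required here. Early scores for patients already treated cannot be recovered.

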Since there is no available studies in this field using the intranasal route and considering that the highest risk times for suicidal behavior are the week after admission to an inpatient psychiatric unit and the week after discharge (Qin & Nordentoft 2005), we aim to investigate the rapid antisuicidal effects of intranasal ketamine in patients with suicidal ideation during depressive episodes with or without recent use of alcohol. We hypothesize that a single dose of intranasal ketamine will induce a rapid, robust and sustained decrease in suicidal ideation in subjects with a comorbid major depressive episode and alcohol dependence relative to only depression and placebo as defined by changes in suicidal ideation scales after 24hrs.

Objectives

Primary objective: To evaluate the rapid antisuicidal effects on a single dose of intranasal ketamine (50mg) in a sample of depression comorbid or not with alcohol abuse compared to placebo.

Secondary objectives:

- To identify clinical variables and dimensions associated with the potential antisuicidal efficacy of intranasal ketamine.
- To identify post-treatment biomarkers associated with the antisuicidal response to ketamine.
- To evaluate the role of recent alcohol abuse in the antisuicidal and antidepressant effects of ketamine
- To identify clinical and biological predictors of response to ketamine
- To evaluate safety and tolerability of intranasal ketamine

Hypothesis:

-Primary: A single dose of ketamine will induce a rapid, robust and sustained decrease in suicidal ideation in subjects with a comorbid major depressive episode and alcohol dependence relative to placebo as defined by change in SSI scale after 24hrs.

-Secondary:

- The antisuicidal efficacy of intranasal ketamine will be independent from its rapid antidepressant efficacy.
- Intranasal ketamine will present superior antisuicidal efficacy in the group with comorbid depression and alcohol compared to depression only.
- Antisuicidal response to ketamine will be correlated with changes in neurotrophic factors and inflammatory markers at one day after ketamine infusion. -Intranasal ketamine (50mg) will be safe and well-tolerated.
- Alcohol use and/or family history of alcohol abuse will be associated with better antisuicidal and antidepressants response to ketamine.

IRB NUMBER: HSC-MS-17-0903

IRB APPROVAL DATE: 10/09/2019

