Analyses of cross-sectional data with missing values will utilize multiple imputation (Proc MI and Proc MIANALYZE, SAS v. 9.3), while longitudinal analyses will rely on maximum likelihood (in the Bayesian context). Multiple imputation, maximum likelihood, and explicitly modeling missing data in the Bayesian approach are all robust to data missing at random. Sensitivity analyses will permit evaluation of the robustness of findings to missing data assumptions. Pattern-mixture modeling methods will address any identified non-ignorable missing data patterns.

Preliminary data analyses will inspect baseline group differences as well as correlations between baseline covariates and specified criterion variables. Baseline covariates demonstrating a correlation

IRB NUMBER: HSC-MS-17-0903

IRB APPROVAL DATE: 10/09/2019

with both predictors and outcome variables, meet criteria for being potential confounders, and will result in two sets of analyses: one in which the relevant variable is included as a covariate and one in which it is not. This will determine the degree to which any group differences might confound conclusions regarding treatment. Analyses will proceed in parallel using conventional, Frequentist and Bayesian approaches. Frequentist results yield the probability of the observed data, or data more extreme, given that the null hypothesis holds. Bayesian results yield the probability that an alternative holds. Eleven patients per group are required using confidence level of 95% (with $P<0.05$, two-tailed) and power 0.8, based on previous studies using ketamine for depression in placebo-controlled studies reporting response rates of 60% with ketamine and 10% with placebo. The study was designed to detect a moderate to large difference ($d=0.7$) between ketamine vs placebo, based on previous studies using IV ketamine (Wilkinson et al 2018). Treatment effects may be also quantified as mean differences between groups and associated effect sizes are based on standardized mean difference (Cohen's d). All statistical tests were two-sided with an alpha set at 0.05. All analyses were performed using SPSS v. 20 (SPSS Inc., USA) and SAS (version 9.2; SAS, Cary, North Carolina).

References

Andrade C. Intranasal drug delivery in neuropsychiatry: focus on intranasal ketamine for refractory depression. *J Clin Psychiatry*. 2015 May;76(5):e628-31.

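### The only stated error rate for the biomarker tests is an unadjusted two-sided 0.05, so large omics screens can be expected to yield false significant markers

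*Combined protocol and SAP*

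**What the plan says.** Study Procedures sets out the laboratory work: "We will also collect blood for the purpose of transcriptional profiling, metabolomics, proteomics". The same sentence goes on to inflammatory measures, among them cytokines and metabolites of the kynurenine pathway. The section then adds brain-derived "neurotrophic factor (BDNF) as well other neurotrophic factors and cytokines in plasma and mRNA expression". No count of analytes is given for any platform.

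On timing, the same section says: "Blood will be collected at the same timepoints, except for 40 minutes and 48 hours post-ketamine". That leaves baseline, 240 minutes and 24 hours, so each marker has at most two post-baseline changes.

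The Objectives list, as secondary, "To identify post-treatment biomarkers associated with the antisuicidal response to ketamine", and separately the search for clinical and biological predictors of response. One secondary hypothesis is more specific: "Antisuicidal response to ketamine will be correlated with changes in neurotrophic factors and inflammatory markers at one day after ketamine infusion". It names two classes of marker and one time point, but no individual marker.

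The text after the list of rating scales limits the ambition: "this investigation is also designed to provide initial data for potential biomarkers of antisuicidal response".

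The Statistics section contains no biomarker analysis. It gives the Spearman coefficient for associations between continuous variables, says that frequentist and Bayesian analyses will run in parallel, and closes with a general rule: "All statistical tests were two-sided with an alpha set at 0.05". No family-wise or false-discovery-rate control, testing order, marker shortlist or validation step appears in the document.

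**The concern.** A single threshold of 0.05 suits a handful of planned comparisons. Applied marker by marker to a screen, it lets through about one in twenty of the markers that have no relation to response. The plan has three omics platforms and further targeted assays, can test two changes per marker, and aims to find both correlates and predictors of response. The number of tests could therefore be large.

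What is at stake is the credibility of the biomarker objectives. The 24-hour hypothesis names no marker, so any one nominal hit among the neurotrophic or inflammatory measures could be presented as support for it. The small sample adds to this. With about 30 ketamine patients, a correlation must be about 0.36 in size to reach p<0.05, so chance hits will look like moderate associations. If the adjustment is chosen only after the results are seen, the reader cannot tell a screened finding from a planned one.

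**Working it through.** **Inputs from the protocol.** Alpha is 0.05, two-sided (Statistics). There are three blood draws, hence at most two post-baseline changes per marker (Study Procedures). The ketamine group has 30 patients (Description of Study Populations).

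**Assumed inputs.** The number m of null tests is not in the documents, so a range is shown. The correlation between tests is not given either. Independence and common correlations of 0.5 and 0.8 (equicorrelated normal test statistics) are used as illustrations.

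**The plan's own figure.** There is none to reproduce. The only sizing figure, 11 per group, concerns clinical response rates and does not bear on the biomarkers.

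**Step 1: expected false positives.** The expected number is 0.05 x m. This holds under any correlation.
- m = 20: 0.05 x 20 = 1
- m = 40: 0.05 x 40 = 2
- m = 1,000: 0.05 x 1,000 = 50

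Testing both post-baseline changes doubles m. For example, 40 markers x 2 changes = 80 tests, and 0.05 x 80 = 4.

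**Step 2: chance of at least one false positive.** Under independence this is 1 - 0.95^m. With correlated tests it is lower.

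| m | Independent | Correlation 0.5 | Correlation 0.8 |
|---|---|---|---|
| 20 | 64% | 42% | 22% |
| 40 | 87% | 57% | 28% |
| 100 | 99.4% | 78% | 36% |
| 1,000 | about 100% | 99.9% | about 58% |

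Correlation bunches the false positives: they occur together in fewer trials, and the average count stays as in step 1.

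**Step 3: what correction costs.** For n = 30, the smallest significant |r| is t / sqrt(n - 2 + t^2), where t is the two-sided critical value on 28 degrees of freedom (an approximation for Spearman).
- Alpha 0.05: t = 2.048, so |r| = 2.048 / sqrt(28 + 4.196) = 0.36.
- Bonferroni over 100 tests, alpha 0.05 / 100 = 0.0005: t = 3.935, so |r| = 3.935 / sqrt(28 + 15.485) = 0.60.

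False-discovery-rate control is less strict than Bonferroni, but its threshold depends on the data and cannot be given in advance.

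**The case against.** The strongest reply is that the plan leaves the omics analysis unspecified and does not prescribe it badly. The Statistics section does not mention blood or biomarkers. Its alpha line is general, stands beside the clinical power statement, and does not forbid adjusted p-values. A reader might infer that the sponsor chose unadjusted testing of every transcript. The documents do not support that. What stands is that 0.05 is the only error rate the plan offers, that it is worded to cover all tests, and that nothing exempts or adjusts the biomarkers.

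Second, the biomarker work is described as initial data, so nominal hits would be leads. This lowers the weight of the point but does not remove it. Biomarkers are also listed objectives with a hypothesis, and no text says that their p-values are descriptive.

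Third, a reader might infer that the 24-hour hypothesis rests on the omics screens. It does not: it covers only neurotrophic and inflammatory markers at one day. That family could be small, but no list says so.

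Fourth, independence is implausible for cytokines or metabolites of one pathway, and correlation lowers the chance of any false hit considerably. This stands for the at-least-one probabilities and leaves the expected counts unchanged.

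Finally, the parallel Bayesian analyses could temper chance findings. No prior, shrinkage or decision threshold is given for markers, so no such protection can be credited.

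**Conclusion.** The point holds as a worthwhile and inexpensive improvement to the secondary analyses. Followed as written, the plan would call about 5% of null markers significant: 1 of 20, 2 of 40, 50 of 1,000. These counts rest on assumed panel sizes but not on independence.

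A reader might go further and conclude that nearly every panel will produce a false hit. That is not supported for small or tightly correlated panels, where the chance can be as low as 22% (20 tests, correlation 0.8). It is reasonable only for large omics platforms, whose size the protocol does not state. Even there, very strong correlation lowers the chance to about 58% for 1,000 tests. Nor does the point reach the primary efficacy conclusion, which does not depend on the biomarkers.

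**What to change.** Add a short biomarker section to the Statistics section before any biomarker data are analysed:

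1. State that the unadjusted 0.05 does not apply to biomarker tests.
2. For the 24-hour hypothesis, name BDNF and a short list of neurotrophic and inflammatory markers, with the test to be used and multiplicity control across that list.
3. Within each omics platform, control the false discovery rate by Benjamini-Hochberg (for example at 5%) across all markers and time points tested.
4. Label every other biomarker result exploratory.

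The change needs no extra patients, samples or assays. It does need the marker list, the families of tests and the time points to be fixed in writing, since no biomarker analysis is set out at present. The price is fewer nominal findings and lower power per marker. With about 30 ketamine patients, the |r| needed would rise from about 0.36 to about 0.60 under Bonferroni for 100 markers, and by less under false-discovery-rate control.

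Multiplicity among the clinical outcomes is a separate matter. This change should not be read as endorsing an unadjusted 0.05 for them.
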